#### **9.2.1.1 Disease specific daily symptom assessment and total symptom score (TSS)**

On a daily basis from V1 and throughout the study, the patient will use an e-diary to:

- Respond to the morning individual rhinosinusitis symptom questions using a 0 to 3 categorical scale (where 0 = no symptoms, 1 = mild symptoms, 2 = moderate symptoms and 3 = severe symptoms) (3):
  - Congestion and/or obstruction.
  - Loss of sense of smell.
  - Anterior rhinorrhea (runny nose).
  - Posterior rhinorrhea (postnasal drip).

The TSS is a composite score (ranging between 0 and 9) consisting of the sum of the following symptoms assessed daily in the morning: nasal congestion/obstruction, decreased/loss of sense of smell, rhinorrhea (average of anterior/posterior nasal discharge).

#### **9.2.1.2 Smell test: University of Pennsylvania Smell Identification Test (UPSIT)**

The UPSIT (UPSIT 40 odorant test) is a rapid and easy-to-administer method to quantitatively assess human olfactory function. The UPSIT shows a high test-retest reliability (r: 0.981) and scores on this test are strongly correlated with the detection threshold for phenyl ethyl alcohol in the same individuals. When the UPSIT is administered in the standardized manner, clinical subjects show a high degree of uniformity in UPSIT performance when tested in different laboratories.

The test will be dispensed to the patient by the study site personnel and consists of 4 booklets, each containing 10 odorants with one odorant per page. The test-time is about 15 min. The stimuli

are embedded in 10-50 (mu) diameter plastic microcapsules on brown strips at the bottom of each page. Above each odorant strip is a multiple-choice question with four alternative words to describe the odor. The subject is asked to release the odorant by rubbing the brown-strip with the tip of a pencil and to indicate which of four words best describes the odor. Thus each subject receives a score out of 40 possible correct answers. The final score will be recorded in the e-CRF. The odorants of the UPSIT test utilized in this study will take into account cultural differences.

The 40-odorant UPSIT is used in over 1500 clinics and laboratories throughout the United States, Canada, South America, and Europe, and has been administered to nearly 200 000 people since its development in the early 1980s. A particular strength of this test is that it provides an olfactory diagnosis based on comparing the patient's test score with normative data, providing a percentile score of an individual relative to his or her age-matched normal group. Furthermore, a clinician can distinguish patients with a normal sense of smell ("normosmia") from those with different levels of reduction ("mild, moderate, and severe microsmia") or loss ("anosmia") (32).

#### **9.2.1.3 Decreased/loss of sense of smell**

The decreased/loss of sense of smell severity is assessed by the patient on a daily basis from V1 and throughout the study, using an e-diary to using a 0-3 categorical scale (where 0 = no symptoms, 1 = mild symptoms, 2 = moderate symptoms and 3 = severe symptoms).

#### **9.2.1.4 Lund-Mackay score**

Lund-Mackay score is a secondary efficacy endpoint in countries other than Japan. Details of this endpoint are presented in [Section 9.1](#).

#### **9.2.1.5 Proportion of patients during the treatment period who receive SCS rescue or are planned to undergo surgery for NP**

##### SCS rescue

Oral steroids for rescue treatment of nasal polyps or for another reason will be prescribed to the patient by the site depending on local legislation/regulation. PROs and a nasal endoscopy should be performed before starting treatment with SCS. The Investigator (or designee) records the date and dosing information (daily dose, duration, INN) on the appropriate page(s) of the e-CRF. Indication for SCS use will be also captured by selecting one or more of the following categories:

1. Nasal polyposis.
2. Asthma.
3. Other respiratory disease (specify).
4. Other ear, nose or throat disease (specify).
5. Other reason (specify).

### Surgery (actual or planned) for NP

For patients who undergo or are planned for sino-nasal surgery for NP, the reason (worsening signs and/or symptoms during the study), the expected and real surgery date, the type and outcome of surgery will be recorded in a specific CRF page. If surgery

- Is performed during the study treatment period, patient and Investigator may decide to continue IMP up to the time of surgery or EOT whichever date comes first. At the time of surgery patients will be permanently discontinued from study treatment and assessed as soon as possible using the procedures normally planned for the EOT Visit and will be instructed to return to the study site as described in [Section 10.3.1](#). An AE or serious adverse event (SAE) page will be completed.
- Is performed during the follow-up the patients will be assessed according to the procedures normally planned for the EOS Visit and will be instructed to return to the study site as described in [Section 10.1.15](#). An AE or SAE page will be completed.
- If surgery is scheduled after the planned end of study, EOS visit will not be delayed. A follow up contact(s) should be performed around the time of planned surgery to document the surgery date and outcome. Surgery data will be collected until e-CRF closure of the trial.

#### **9.2.1.6 22-Item sino-nasal outcome test (SNOT-22)**

The SNOT-22 is a validated questionnaire to assess the impact of chronic rhinosinusitis on HRQoL ([Appendix B](#)). The SNOT-22 has 22 items on a 5-category scale applicable to sino-nasal conditions and surgical treatments. The range of the global score is 0-110 and a minimal important difference (MID), the smallest difference between clinical trial arms mean change from baseline (point estimates) that will be interpreted as important of 8.9 ([33](#)). Lower scores indicate less impact and the recall period is past 2 weeks. There are 5 domains that can be described within SNOT-22, including nasal, ear, sleep, general and practical, and emotional.

#### **9.2.2 Other secondary endpoints**

For the assessment of other secondary endpoints see analyses of efficacy endpoints, ([Section 11.4.2.4](#)).

##### **9.2.2.1 SCS dose and number of courses**

Total SCS rescue dose prescribed (in mg/year) during the study period and total SCS rescue intake in days and courses during the study period could be derived based on SCS dose prescribed and intake days of SCS during the study, recorded in eCRF pages.

A course of SCS is considered continuous if treatment is separated by less than 7 days. Various doses of systemic corticosteroids will be converted to prednisone-equivalent OCS.

### **9.2.2.2 Visual analogue scale**

The visual analogue scale (VAS) for rhinosinusitis is used to evaluate the total severity (2). Rhinosinusitis disease can be divided into MILD, MODERATE and SEVERE based on total severity VAS score (0 to 10 cm):

- MILD = VAS 0 to 3.
- MODERATE = VAS >3 to 7.
- SEVERE = VAS >7 to 10.
- The patient is asked to indicate on a VAS the answer to the question below:

“How troublesome are your symptoms of your rhinosinusitis”

The VAS ranks from 0 (Not troublesome) to 10 (Worst thinkable troublesome) ([Appendix D](#)).

### **9.2.2.3 Nasal peak inspiratory flow**

Nasal peak inspiratory flow (NPIF) evaluation represents a physiologic measure of the air flow through both nasal cavities during forced inspiration expressed in liters per minute. The NPIF is the best validated technique for the evaluation of nasal flow through the nose. Nasal inspiration correlates most with the subjective feeling of obstruction and is the best validated technique for monitoring nasal flow in clinical trials.

On V1 patients will be issued an NPIF meter for recording morning (AM) NPIF. Patients will be instructed on the use of the device, and written instructions on the use of the NPIF meter will be provided to the patients. In addition, the Investigator will instruct the patients on how to record the following variables in the e-diary on a daily basis.

- AM NPIF performed within 15 minutes after arising (before 12 noon) prior to taking MFNS.

Three NPIF efforts will be performed by the patient; all 3 values will be recorded by the patient in the e-diary, and the highest value will be used for evaluation. The procedure takes about 5 minutes.

Baseline AM NPIF will be the mean AM measurement recorded for the 7 days prior to the first dose of IMP. If less than 4 measurements are collected during the 7 days, the average of the most recent 4 prior to randomization during the run-in period will serve as the baseline.

The NPIF will be performed daily from V1 to Week 24 (V8). After V8 the NPIF will be performed every 4 weeks.

The nasal flow is expressed in liter per minute, and consecutive measurements are performed. Taking the best of 3 outcomes with less than 10% variation is considered to be the best means of expression of the result (32).

#### **9.2.2.4 Asthma Control Questionnaire, 6-question version (ACQ-6) in those patients comorbid with asthma**

The asthma control questionnaire-6 (ACQ-6) was designed to measure both the adequacy of asthma control and change in asthma control which occurs either spontaneously or as a result of treatment. Only patients with co-morbid asthma will be asked to complete the questionnaire in the e-diary during clinic visits. Patients should complete the questionnaire before the spirometry test.

The asthma control questionnaire-6 (ACQ-6) has 6 questions which assess the most common asthma symptoms:

- Frequency in past week awoken by asthma during the night.
- Severity of asthma symptoms in the morning.
- Limitation of daily activities due to asthma.
- Shortness of breath due to asthma.
- Frequency of wheezing, and
- Short-acting bronchodilator use.

Patients are asked to recall how their asthma has been during the previous week and to respond to the symptom questions on a 7-point scale (0 = no impairment, 6 = maximum impairment) (see [Appendix E](#)).

A global score is calculated: the questions are equally weighted and the ACQ-6 score is the mean of the 6 questions and, therefore, between 0 (totally controlled) and 6 (severely uncontrolled). Higher score indicates lower asthma control. Patients with a score below 1.0 reflect adequately controlled asthma and patients with scores above 1.0 reflect inadequately controlled asthma. On the 7-point scale of the ACQ-6, a change or difference in score of 0.5 is the smallest change that can be considered clinically important, corresponding to the Minimal Clinically Important Difference (MCID) defined by the developer.

Measurement properties such as reliability, ability to detect change have been documented in the literature ([34](#)).

#### **9.2.2.5 Health related quality of life (HRQoL)**

##### **9.2.2.5.1 Euro-QOL-5D**

The European quality of life-5D scale (EQ-5D) ([Appendix C](#)) is a standardized HRQoL questionnaire developed by the EuroQoL Group in order to provide a simple, generic measure of health for clinical and economic appraisal ([35](#)). EQ-5D is designed for self-completion by patients.

The EQ-5D essentially consists of 2 pages: the EQ-5D descriptive system and the EQ VAS. The EQ-5D descriptive system comprises 5 dimensions: mobility, self-care, usual activities, pain/discomfort and anxiety/depression. Each dimension has 5 levels: no problems, slight problems, moderate problems, severe problems, and extreme problems. The EQ VAS records the

respondent's self-rated health on a vertical VAS. The EQ VAS 'thermometer' has endpoints of 100 (best imaginable health state) at the top and 0 (worst imaginable health state) at the bottom.

### 9.3 EXPLORATORY ENDPOINTS:

- Healthcare resource utilization.
- Proportion and time-to-event of patients with SCS rescue for nasal polyps.
- Proportion and time-to-event of patients who have or are planned for surgery of nasal polyps.
- Change from baseline in decreased/loss of sense of taste symptom severity.
- SNOT-22 items: "decreased sense of smell/taste", "difficulty falling asleep", "wake up at night", "lack of a good night's sleep", "wake up tired", "fatigue", and "reduced productivity".
- Pharmacodynamic biomarkers in blood and urine.
- [REDACTED]
- [REDACTED]
- FEV1, FVC and FEF 25-75 in patients with asthma.
- Efficacy endpoints for the sub-group of patients with SCS use in the year prior to study Visit 1.
- Patient reported outcomes including HRQoL scale (EQ5D-5L, Index Score)

#### 9.3.1 Spirometry

Spirometry will be performed at local level (study site or another facility) in the morning after withholding the last dose of salbutamol/albuterol or levosalbutamol/levalbuterol for at least 6 hours. FEV1, forced vital capacity (FVC) and forced expiratory flow at 25% to 75% of forced vital capacity (FEF 25-75) will be determined at the designated treatment visits. The results of FEV1 (% of predicted normal), FVC and FEF 25-75 should be recorded in the e-CRF anytime during run-in period (before V2) for all patients and in patients with asthma for the other scheduled visits during the randomized treatment period.

Whenever possible, the same spirometer and standard spirometric techniques, including calibration, will be used to perform spirometry at all visits and, the same person should perform the measurements.

### 9.4 SAFETY ENDPOINTS

#### 9.4.1 Adverse events

Refer to [Section 10.4](#) to [Section 10.6](#) for details.

#### **9.4.2 Laboratory safety variables**

The clinical laboratory data consist of blood and urine analysis (including serum hematology and clinical chemistry). Clinical laboratory values will be analyzed after conversion into standard international units. International units will be used in all listings and tables.

- Hematology includes: hemoglobin, hematocrit, platelet count, total white blood cell count with 5-part differential count, differential count, and total red blood cell count.
- Serum chemistry includes: creatinine, blood urea nitrogen, glucose, uric acid, total cholesterol, total protein, albumin, total bilirubin (in case of values above the normal range, differentiation in conjugated and non-conjugated bilirubin), ALT, aspartate aminotransferase, alkaline phosphatase, lactate dehydrogenase, electrolytes (sodium, potassium, chloride), bicarbonate, and CPK.
- HIV screening (Anti-HIV-1 and HIV-2 antibodies)
- Anti-nuclear antibody (ANA). Note: Anti-ds DNA antibody will be tested if ANA is positive ( $\geq 1:160$  titer).

#### **9.4.3 Hepatitis screening**

Hepatitis screening: HBsAg, hepatitis B surface antibody (HBsAb), HBcAb including HBcAb IgM and total, hepatitis C virus antibodies (HCVAbs). In case of results showing HBsAg (negative) and HBcAb total or HBcAb IgM (positive), a HBV DNA testing must be performed prior to randomization to determine eligibility. In case of results showing HCVAbs (positive), a HCV RNA testing must be performed prior to randomization to determine eligibility.

For patients in Japan (or other countries/regions if there is local regulatory requirement) who are HBsAg negative and HBsAb positive at V1, Hepatitis B viral load will be tested at V2, V7, V8, and V10.

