- n* Vital signs, including blood pressure (mmHg), heart rate (beats per minute), respiratory rate (breaths per minute), body temperature (degrees Celsius) and body weight (kg) will be measured at the screening and randomization visits (V1 and V2) and subsequent visit pre-specified in the flow-chart. Height (cm) will be measured at screening (V1) only. Vital signs will be measured prior to receiving IMP at the clinic visits in the sitting position using preferably the same arm at each visit.
- o* Hematology: hemoglobin, hematocrit, platelet count, total white blood cell (WBC) count with five-part differential count, and total red blood cell count. Serum chemistry: creatinine, blood urea nitrogen, glucose, uric acid, total cholesterol, total protein, albumin, total bilirubin (in case of values above the normal range, differentiation in conjugated and nonconjugated bilirubin), alanine aminotransferase, aspartate aminotransferase, alkaline phosphatase, lactate dehydrogenase, electrolytes (sodium, potassium, chloride), bicarbonate, and creatine phosphokinase. Clinical laboratory testing at V1 includes hepatitis screen covering hepatitis B surface antigen (HBsAg), hepatitis B surface antibody (HBsAb), hepatitis B core antibody (HBcAb) including HBcAb IgM and total, hepatitis C virus antibodies (HCVAb), Human Immunodeficiency Virus (HIV) screen (anti-HIV-1 and HIV-2 antibodies) and antinuclear antibody (ANA). In case of results showing HBsAg (negative), and HBcAb total or HBcAb IgM (positive), an HBV DNA testing may be performed prior to randomization to rule out a false positivity if the Investigator believes the patient is a false positive, or to clarify the serological status if the Investigator finds it unclear to interpret in absence of known HBV infection. In case of results showing HCV Ab (positive), an HCV RNA testing may be performed to rule out a false positivity, if the Investigator believes the patient is a false positive. Note: Anti-ds DNA antibody will be tested if ANA is positive ( $\geq 1:160$  titer). Tuberculosis local testing at baseline would be performed on a country by country basis according to local guidelines if required by regulatory authorities or ethic committees.
- p* This is only applicable for patients in countries/regions where there is local regulatory requirement who are HBs Ag negative and HBs Ab positive at the run-in period visit.

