- E 27. Active hepatitis or patients with positive or indeterminate hepatitis B surface antigen (HBsAg), hepatitis B core antibody (HBcAb) (confirmed with presence of hepatitis B virus [HBV] deoxyribonucleic acid [DNA]), or positive hepatitis C virus antibody (HCVAb) (confirmed with presence of HCV ribonucleic acid [RNA]) at V1.
- E 28. Patients with the following liver injury related criteria at V1:
- Clinically significant/active underlying hepatobiliary disease.
- OR,**
- Alanine aminotransferase (ALT) >3 upper limit of normal (ULN).
- E 29. Abnormal laboratory values at V1:
- Creatine phosphokinase (CPK) >10 ULN
- OR,**
- Platelets <100 000 cells/mm^3.
- OR,**
- Eosinophils >1500 cells/mm^3.
- E 30. Conditions/Situations such as: Patients considered by the Investigator or any sub-Investigator as inappropriate for this study for any reason, eg.:
- Those deemed unable to meet specific protocol requirements, such as scheduled visits.
  - Those deemed unable to administer or tolerate long-term injections as per the patient or the Investigator.

- Presence of any other conditions (eg, geographic, social....) actual or anticipated, that the Investigator feels would restrict or limit the patient's participation for the duration of the study.

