- Perform spirometry within the time period between V1 and V2, for all patients and ensure that patients with co-morbid asthma have FEV1 $>50\%$ . Spirometry will be performed after the last dose of salbutamol/albuterol or levosalbutamol/levalbuterol has been withheld for at least 6 hours.
- Obtain blood samples for screening clinical laboratory determinations:
  - Hematology (see [Section 9.4.2](#) for details),

- Serum chemistry (see [Section 9.4.2](#) for details).
- Obtain blood samples for hepatitis screen (HBsAg, HBsAb, HBcAb, HCVAb, HIV screen (Anti-HIV-1 and HIV-2 antibodies) and anti-nuclear antibody (ANA). In case of results showing HBsAg (negative), and HBcAb total or HBcAb IgM (positive), an HBV DNA testing may be performed prior to randomization to rule out a false positivity if the Investigator believes the patient is a false positive, or to clarify the serological status if the Investigator finds it unclear to interpret in absence of known HBV infection. In case of results showing HCV Ab (positive), an HCV RNA testing may be performed to rule out a false positivity, if the Investigator believes the patient is a false positive.
  - Note: Anti-ds DNA antibody will be tested if ANA is positive ( $\geq 1:160$  titer).
- Obtain serum  $\beta$ -HCG pregnancy test if WOCBP.
- Perform chest X-ray if no chest imaging (X-ray, CT, MRI) available within the previous year as per local standard of care or if there is local requirement.
  - Note for Japan: According to the request from the health authority, chest X-ray should be performed at V1 if there is no chest imaging (Chest X-ray, CT, MRI) available within 3 months prior to V1 to exclude patients with suspected active or untreated latent tuberculosis.
- Perform nasal endoscopy and send to Central Reader.
- Dispense e-diary/NPIF meter, provide instructions for daily use, and remind patient to bring the device to the next visit.
- NIMP:
  - Dispense MFNS for use as mandatory background therapy throughout the study. Ensure that the patient has sufficient quantity for dosing up until the next visit, knowing that one MFNS bottle contains sufficient doses for either 2 weeks of BID treatment or 4 weeks of QD treatment. Instruct patient on MFNS use and to record daily administration in the e-diary.
- Start AE reporting.
- Review and record all medication use with start date and dose in e-CRF.
  - Check for use of prohibited medications.

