#### **10.6.4 Elevated liver function tests**

No pre-clinical or clinical data has suggested any hepatic toxicity of dupilumab; however, as a general consideration of clinical development, the administration of immunosuppressant or immunomodulating agents may represent an additional risk factor for hepatotoxicity.

In order to closely follow liver function tests (LFT), assessment of total protein, albumin, total bilirubin, ALT, aspartate aminotransferase, and alkaline phosphatase are measured as part of the

clinical laboratory testing. Clinical laboratory testing at V1 adds hepatitis screen (HBsAg, HBsAb, HBcAb, HCVAb. Active hepatitis or patients with positive or indeterminate HBsAg, HBcAb or positive HCVAb at V1 are excluded from the study.

Guidance for the investigation of elevated LFTs is provided in [Appendix G](#).

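### Hepatitis B and C eligibility is stated in incompatible ways: the same antibody-positive patient can be excluded, tested first, or arguably randomized untested

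*Protocol*

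**What the plan says.** Protocol 9.4.3 (Hepatitis screening) sets the trigger, "In case of results showing HBsAg (negative) and HBcAb total or HBcAb IgM (positive", and states that in this case "a HBV DNA testing must be performed prior to randomization to determine eligibility". It imposes the same duty for HCV RNA when HCVAb is positive.

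Protocol 1.2, footnote o, has the same trigger but a different status for the test, which there depends on suspicion of a spurious result ("an HBV DNA testing may be performed prior to randomization to rule out a false positivity if the Investigator believes the patient") or on unclear serology with no known infection. Protocol 10.1.1 (Visit 1) repeats this: "an HBV DNA testing may be performed prior to randomization to rule out a false positivity". Both also make HCV RNA testing optional.

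E 27 in Protocol 7.2.3 lists HBcAb as an exclusion with the qualifier "confirmed with presence of hepatitis B virus [HBV] deoxyribonucleic acid [DNA", and qualifies HCVAb in the same way by HCV RNA.

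Protocol 10.6.4 (Elevated liver function tests) states the exclusion with no such qualifier: "Active hepatitis or patients with positive or indeterminate HBsAg, HBcAb or positive HCVAb at V1 are excluded from the study".

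SAP 2.1.4.3 also makes both tests optional. For HBV DNA it adds a condition that the Protocol does not have: HBsAb must be negative too.

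**The concern.** On one trigger the test cannot be both compulsory and discretionary, and HBcAb cannot exclude both by itself and only when DNA is found. The stated purpose differs as well: in 9.4.3 the test decides eligibility, while in footnote o and 10.1.1 it clears up a suspected false positive or an unclear result.

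This is a safety screen. Protocol 10.6.4 itself describes immunomodulating agents as a possible added risk for hepatotoxicity, and Protocol 4.5 relies on excluding patients at high risk of reactivating infection. The rescreening text in 10.1 allows no waivers, so the wording of the criterion settles who enters. With about 130 sites, different readings could admit different patients and produce avoidable eligibility deviations.

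**Working it through.** No arithmetic applies. The check sets each statement of the rule side by side and follows one patient through them: HBsAg negative, HBcAb positive, normal ALT, no known liver disease.

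| Place | HBV DNA test | What excludes |
|---|---|---|
| Protocol 9.4.3 | Required before randomization | Not stated there; the result decides eligibility |
| Protocol 1.2 footnote o; 10.1.1 | Optional, at the Investigator's judgment | Not stated there |
| Protocol 7.2.3, E 27 | Not mentioned as a procedure | HBcAb confirmed by HBV DNA |
| Protocol 10.6.4 | Not mentioned | HBcAb positive or indeterminate, by itself |
| SAP 2.1.4.3 | Optional, and only if HBsAb is also negative | Not stated there |

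Combining the rows gives three outcomes:

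1. **10.6.4 alone.** The patient is excluded on serology. A negative DNA result would not help.
2. **9.4.3 with E 27.** The patient is tested, excluded if DNA is present, and otherwise eligible.
3. **Footnote o or 10.1.1 with E 27.** The test may be omitted. Without a result, DNA presence is not confirmed, so E 27 as worded is not met and the patient could be randomized untested.

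For HCVAb the pattern is the same: RNA test required in 9.4.3, optional in footnote o, 10.1.1 and the SAP, RNA confirmation needed in E 27, antibody alone sufficient in 10.6.4.

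Next, does any other provision remove the ambiguity?

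- **Other exclusions.** Active hepatitis (E 18, E 27), hepatobiliary disease or raised ALT (E 28) and Investigator discretion (E 30) give no rule for a clinically silent HBcAb-positive patient without a DNA result.
- **Viral-load monitoring.** In 9.4.3 and footnote p it covers HBsAg-negative, HBsAb-positive patients in Japan or where local rules require it. The HBsAb-negative, HBcAb-positive pattern that the SAP singles out is not covered. At Visit 2 (10.1.2) this sample is listed after the randomization call, so it does not work as an entry check.
- **Rescreening.** Section 10.1 bars rescreening after a positive hepatitis test, without saying whether that means serology or nucleic acid.

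**The case against.** The best defense is that the sections can be reconciled. A site that always tests complies with both the compulsory and the optional text, and 9.4.3 with E 27 then gives a workable rule. Section 7.2 holds the governing list of criteria, while 10.6.4 is safety background that shortens E 27. The optional wording, being about false positives, can also be read as excluding the patient by default unless the test clears them. No section directs a site to randomize an untested patient. Sites do not screen from the SAP. On-study liver tests, the ALT and bilirubin discontinuation criteria (10.3.3) and ALT reporting as an event of special interest (10.4.1.3) add protection.

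Part of this stands. The untested outcome is an inference from two sections read together, the SAP mismatch is secondary, and the documents support saying that sites could diverge, not that they will. The documents also do not show whether a laboratory instruction already triggers the nucleic-acid test, so neither answer can be assumed.

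It does not resolve the conflict. The always-test reading still clashes with 10.6.4, which excludes even a DNA-negative patient. The default-exclusion reading fits 10.6.4 but clashes with E 27, which requires DNA confirmation. Two plausible and opposite readings of a criterion that cannot be waived are themselves the defect. Monitoring after entry does not say who may enter.

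**Conclusion.** The concern holds. Two conflicts are direct: 9.4.3 against footnote o and 10.1.1 on whether the test is required, and E 27 against 10.6.4 on whether antibody positivity alone excludes. The untested-randomization outcome depends on combining the optional test with E 27 and is a possible reading, not an instruction.

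The consequence is for participant safety and uniform eligibility. No sample size, power, alpha or endpoint definition is affected. Every HBcAb-positive or HCVAb-positive screened patient falls under the ambiguity; without a prevalence in the documents, no count can be given. It should be corrected. It is an internal contradiction, and nothing here judges which of the rules is clinically right.

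**What to change.** Reconcile Protocol 9.4.3, 10.1.1, footnote o of 1.2, E 27, 10.6.4 and SAP 2.1.4.3 into one rule, worded identically or replaced by a reference to E 27. The rule should state:

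- the serologic pattern that triggers the nucleic-acid test, including the role of HBsAb and of indeterminate results;
- whether the test is required before randomization, and the eligibility status of a patient with no result;
- whether antibody positivity alone excludes, for HBcAb and for HCVAb;
- which result counts as positive for the rescreening bar in 10.1.

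The sponsor chooses the content. The cost is Protocol and SAP wording and, at most, a reflex-test instruction to the central laboratory.
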